Application of Economics & Social psychology to improve Opioid Prescribing Safety (AESOPS) Trial 2 is a multi-site randomized trial that takes place among a clinic organization in Los Angeles, California (AltaMed Health Services) and one in Chicago, Illinois (Northwestern University). Participants in the trial are clinicians. Observations are visits where opioids are prescribed. Clinicians are randomized to receive either: 1) guidelines on opioid prescribing, or 2) information on an opioid harm experienced by one of their patients (non-fatal or fatal overdose). In Los Angeles, fatal overdose letters are already required by the County, therefore, only non-fatal overdose letters will be sent to clinicians in Los Angeles. These will be signed by the County Public Health Officer. In Chicago, Illinois, both types of letters will be sent. Outcomes are milligram morphine equivalents ordered by each participating clinician per week. A secondary outcome is referrals to medication assisted treatment. These data are collected from the electronic health record systems at AltaMed and Northwestern Medical Center. Determining overdoses involves connecting data on overdoses between hospital systems, or in the case of Illinois, state vital records. More specifically, non-fatal overdoses in Los Angeles connect opioid prescribing at AltaMed with Los Angeles County emergency department data (See Appendix 1, Figure 1a), non-fatal overdoses at Chicago's Northwestern University involve a search of the internal database that connects that University's outpatient clinic data with emergency department data (See Appendix 1, Figure 1b), and fatal overdoses among patients at Northwestern connect data from that institution with Illinois State Vital records (Illinois Department of Public Health (IDPH); See Appendix 1, Figure 1c). A pilot study was originally approved for the data exchange in Figure 1c and the secure data sharing exercise was successful.

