1. Clinicians randomized to the overdose notification group will exhibit a greater reduction in weekly MME from the pre- to post-period compared to clinicians randomized to the control group for fatal and non-fatal overdoses.
2. Among the clinicians who prescribed at least one opioid in the study period, those randomized to the overdose notification group will exhibit a greater reduction in the proportion of a clinician's patients prescribed at least 50 daily MME from the pre- to post-period compared to clinicians randomized to the control group for fatal and non-fatal overdoses.

b) Number of subjects:

AltaMed Health Services is a private health system in Los Angeles, California. AltaMed has 35 clinics with 134 clinicians with 17,674 such patients. Clinicians meeting inclusion criteria will be enrolled in the study. Northwestern Medicine is a regional health system affiliated with an academic medical center located in the Chicago region of Illinois and includes 60 primary care clinics that contain 387 clinicians with 12,552 patients using chronic opioid therapy for noncancer pain—on opioids for greater than three months.

c) Mechanism for subject selection or exclusion:

Eligible physicians and patients will be identified using outpatient opioid prescribing data

from electronic medical records. A clinician is eligible for inclusion if: 1) s/he prescribed a qualifying scheduled drug to a patient in the 12 months prior to their fatal or non-fatal overdose 2) the patient is 18 years old or older at the time of the overdose, 3) s/he practices within a health system enrolled in the study, and 4) the overdose occurs during the 12-month observation period.

A patient is eligible for identification in a physician notification if s/he (a) has been prescribed an opioid by an eligible clinician (b) has a documented overdose event in EHR or mortality data. Patients without overdose events will be excluded. Patients with fatal overdoses in Los Angeles County will be excluded to avoid redundancy with existing notification practices.

[figure not shown]
d) Duration of intervention:

The duration of the overdose notification intervention is one day.

e) Total duration which study will be performed (data collection, intervention, and analysis period):

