Non-Fatal Overdose Records: Northwestern University. A one time data extract will be generated at the beginning of the study, looking back 24 months to identify clinicians who prescribed a qualifying scheduled drug to a patient in the 12 months prior to their non-fatal overdose. The list of patients with outpatient opioid prescriptions will be used to retrieve overdose records that occur within the 12 month observation period. Emergency department and outpatient records at Northwestern are secured in the same EHR. The list will be delivered to Northwestern study staff to prepare notification letters.

Quarterly Fatal Overdose Records. Opioid-related death data will be gathered from the Illinois Department of Public Health (IDPH). Each quarter, Northwestern study personnel will securely transfer IDPH a list of identifiers for patients who received an opioid prescription at a participating clinic. IDPH will use this information to identify if the patient is deceased. If so, IDPH will send back the date of death, cause of death, and whether the death was opioid-related via a secure file transfer process to Northwestern Medicine. IDPH will not send back information if a patient is not deceased. Analysts at Northwestern Medicine will link opioid-related decedents to identify opioid prescriptions and prescribers. The list of patients with fatal overdose will be returned to Northwestern Medicine for preparation of notification letters.

As described above, each system's enterprise software and identifiers will be employed to match patients and their providers across settings.

Allocation Data Set and Study Identifiers. Each patient and prescriber will be assigned a unique study identifier based on outpatient data before overdose data is added. The

randomization and allocation procedure described in Experimental Procedures (below) will be applied by the Los Angeles Department of Health Services and Northwestern Study Staff to create the final list of notifications.

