$$(pills)_{ijk}^* = \beta_1 + \beta_2 Time_{ij} + \beta_3 (Time_{ij} - t^*) + \beta_4 Group_i + \beta_5 Overdose Type_k + \beta_6 Group_i * Overdose Type_k + \beta_7 Time_{ij} * Group_i + \beta_8 (Time_{ij} - t^*) * Group_i + \beta_9 Time_{ij} * Overdose Type_k + \beta_{10} (Time_{ij} - t^*) * Overdose Type_k + \beta_{11} Time_{ij} * Group_i * Overdose Type_k + \beta_{12} (Time_{ij} - t^*) * Group_i * Overdose Type_k + \eta + \delta_{i(k)} + error$$

where $(pills)_{ijk}^*$ denotes the dependent variable for clinician i in week j , $Time_{ij}$ is the study week indexed by j , t^* is the spline knot for the start of the intervention, $(Time_{ij} - t^*)$ is a truncated line function that is equal to $(Time_{ij} - t^*)$ when $Time_{ij} > t^*$ and 0 otherwise to allow for nonlinear trends in prescribing following the intervention, $Group_i$ is dichotomous for the overdose notification intervention group, $Overdose Type_k$ is dichotomous for a fatal overdose, η is the clinic random effect, and $\delta_{i(k)}$ is the random effect for each clinician i who prescribed to patient k who suffered an overdose.

The mixed logistic regression model for our secondary outcomes is shown in Eq. 2:

$$(high dose Rx)_{ijk} = \beta_1 + \beta_2 Time_{ij} + \beta_3 Group_i + \beta_4 Overdose Type_k + \beta_5 Group_i * Overdose Type_k + \beta_6 Time_{ij} * Group_i + \beta_7 Time_{ij} * Overdose Type_k + \beta_8 Time_{ij} * Group_i * Overdose Type_k + \eta + \delta_{i(k)} + error$$

where $(high\ dose\ Rx)_{ijk}$ is whether the visit had a high dose prescription of 50 MME or greater (yes vs. no) for clinician i , $Time_{ij}$ is the study period (pre- vs. post-intervention) indexed by j , $Group_i$ is dichotomous for the overdose notification intervention group, $Overdose\ Type_k$ is dichotomous for a fatal overdose, η is the clinic random effect, and $\delta_{i(k)}$ is the random effect for each clinician i who prescribed to patient k who suffered an overdose. We will compute the estimated pre- to post-intervention change in the mean proportion of high dose patient visits for each of the four intervention groups: nonfatal control, nonfatal letter, fatal control, fatal letter. The proportion will be calculated by dividing the total number of patient visits where an opioid of at least 50 MME was prescribed by the total number of opioid prescriptions.

E. Privacy of Individuals and Confidentiality of Data

We will utilize two types of data for this study:

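### Eq. 2 treats one patient's repeat opioid visits as independent, so its standard error for Hypothesis 2 is not valid and the direction of the error is not known in advance

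*Combined protocol and SAP*

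**What the plan says.** Hypothesis 2 (Section B.a, under the primary hypotheses) predicts, for the letter arm, a "greater reduction in the proportion of a clinician's patients prescribed at least 50 daily MME from the pre- to post-period". The Study Synopsis in the same section lists this outcome as secondary, and so does Section D: "The mixed logistic regression model for our secondary outcomes is shown in Eq. 2".

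The dependent variable in Eq. 2 "is whether the visit had a high dose prescription of 50 MME or greater (yes vs. no) for clinician i". Time is binary (pre or post), so the letter effect is a difference in pre-to-post change. There are two random effects. The first, η, "is the clinic random effect, and" the second, δ, "is the random effect for each clinician i who prescribed to patient k who suffered an overdose". Section D gives no patient-level term, robust variance, GEE or sensitivity model for this outcome.

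On the data, the Study Synopsis says "Observations are visits where opioids are prescribed". Section B.b describes Northwestern as having "12,552 patients using chronic opioid therapy for noncancer pain", meaning opioid use for more than three months. Section B.e sets two six-month periods.

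**The concern.** A patient on continuing opioid therapy will usually have several opioid visits in six months, often at much the same dose. Given the clinician, those yes/no outcomes are correlated. Nothing in Eq. 2 represents this: k is the overdose patient who defines the cluster, so it does not link visits by the clinician's other patients, and the error term does not either.

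Two consequences pull in opposite directions.

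- Repeat visits within a period make the apparent sample larger than the real one, so the standard error is too small.
- A patient seen in both periods at a stable dose largely cancels out of the pre-to-post change. Eq. 2 gives no credit for that pairing, so the standard error is too large.

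The problem exists even if no clinician and no overdose cluster differs from another in its change over time, so it is separate from clustering at those levels. At stake are the p-value and interval for Hypothesis 2. Eq. 1 is not touched by this point, because its observations are clinician-weeks.

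**Working it through.** The documents give no alpha, standard error or intraclass correlation for Eq. 2, so there is no planned figure to reproduce.

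**Inputs from the documents.** Outcome, random effects and binary period: Section D. Six-month periods: Section B.e. Patients per clinician: 12,552/387 = 32.4 (Northwestern) and 17,674/134 = 131.9 (AltaMed), Section B.b.

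**Assumed inputs.** Two-sided 5% test; m = 6 visits per patient per period on average; ρ = within-patient correlation of high-dose status in a period (0.3 to 0.9); f = share of patients seen in both periods (1 minus turnover); c = correlation of a continuing patient's status between periods (10% redrawn gives c = 0.9); s² = variance of the visit count, independent between periods.

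**Step 1: variance ratio.** Per patient, the variance of a period total is proportional to m(1−ρ) + (m² + s²)ρ. The covariance between periods is m²·f·c·ρ. Eq. 2 assumes m and 0 respectively. Hence

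ratio = true variance / model variance = 1 + (m−1)ρ + (s²/m)ρ − m·f·c·ρ

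false-positive rate = 2[1 − Φ(1.96/√ratio)]

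Patients per clinician drop out of the ratio.

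**Step 2: direction.** Take equal counts (s² = 0), m = 6, ρ = 0.5, c = 1.

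- f = 1: 1 + 2.5 − 3.0 = 0.5, rate 0.6%
- f = 0.8: 1 + 2.5 − 2.4 = 1.1, rate 6.2%
- f = 0.6: 1 + 2.5 − 1.8 = 1.7, rate 13.3%
- f = 0: 1 + 2.5 = 3.5, rate 29.5%

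Break-even is f·c = (m−1)/m = 5/6. Above that the test is conservative; below it, anti-conservative.

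**Step 3: effect of irregular visits.** Take ρ = 0.9 and c = 0.9. For varying counts use 1 + Poisson(5), so s² = 5 and the added term is (5/6)(0.9) = 0.75.

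| Turnover | Ratio, equal counts | Rate | Ratio, varying counts | Rate |
|---|---|---|---|---|
| 0% | 5.5 − 4.86 = 0.64 | 1.4% | 1.39 | 9.6% |
| 20% | 5.5 − 3.888 = 1.612 | 12.3% | 2.362 | 20.2% |
| 40% | 5.5 − 2.916 = 2.584 | 22.3% | 3.334 | 28.3% |

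**Step 4: simulation under no letter effect.** A logistic model with a clinician random intercept was fitted by quadrature to data from 200 clinicians with 32 patients each, 15% high-dose, and 10% of continuing patients' status redrawn. Several independent sets of 200 to 600 runs gave these false-positive rates:

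| Turnover | Equal counts | Varying counts |
|---|---|---|
| 0% | 1% to 2% | 9% to 13% |
| 20% | 10.5% to 12.5% | 18% to 22.5% |
| 40% | 18.5% to 22.5% | 24.5% to 29% |

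With no turnover and no redraw, the rate was 0% with equal counts and 3% to 4% with varying counts. With three visits and 30% turnover it was 7% and 16%. One set in the varying column (13%, 22%, 29%) did not record its visit-count rule; it fits that column and not the other.

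A different data model (30 patients per clinician, six equal visits, normally distributed patient effects on the logit scale with ρ about 0.24 or 0.48, no drift) gave 2.4% or 0.2% at full overlap, 6.8% or 7.6% at f = 0.8, 12.2% or 19.8% at f = 0.5, and 18.0% or 29.0% at f = 0.

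**Step 5: an alternative test.** A two-sample comparison of clinician-level pre-to-post changes, under that second data model, gave 4.5% to 5.6% in ten six-visit scenarios of 4,000 runs each. In small 200-run checks it ranged from 2% to 8%.

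**Limits.** The simulations leave out overdose type and the clinic effect, so they test one group-by-period term. In Eq. 2 that coefficient is the nonfatal effect. Clinicians were generated as independent, without overdose clusters.

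**The case against.** The strongest reply is that the feature showing repeat visits, chronic therapy, also suggests a stable panel seen in both periods. There Eq. 2 errs on the safe side. This stands: with equal visit counts and no turnover the simulated rate was about 2% or less, and the harm would be lost power, not false positives.

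It also stands that no driving input is in the documents. The figures of 32 and 132 patients are system-wide averages, while enrolled clinicians qualify through an overdose patient. The Study Synopsis counts all visits with an opioid prescription, so short-term patients contribute too. They add turnover and fewer visits each.

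A reader might infer that monthly visits by themselves push the error rate to 13% to 29%. The documents do not support that. With exactly six visits per patient and no turnover the test is conservative. Rates in that range need turnover or substantial dose change; to reach 13% without turnover, at 10% redraw, visit counts must also vary between a patient's two periods.

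A reader might also infer that patient random intercepts are the obvious cure. That model was not fitted in this check. If status hardly varies within a patient, its variance components become very large and its coefficient is an odds ratio conditional on the patient, whereas Section D promises the change in the mean proportion.

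None of this removes the defect. Whether the standard error is too small or too large depends on quantities the plan does not state.

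**Conclusion.** The point holds as a defect in the variance of Eq. 2, with unknown direction. Followed as written, the only model given for Hypothesis 2 treats repeat visits as independent given clinic and clinician, and ignores the pairing of continuing patients.

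Under the assumptions listed (200 clinicians, 32 patients each, 15% high-dose, about six visits per period, 10% of continuing patients' status redrawn unless stated), a nominal 5% test has a true size of:

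- about 2% or less with a stable panel and equal visit counts;
- about 10% to 22% with 20% to 40% turnover and equal counts;
- about 9% to 29% with 0% to 40% turnover and counts that vary between periods.

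These figures are illustrations, not predictions for this trial. The change should be made before analysis. Its weight is limited by the outcome's mixed status: primary in the list of hypotheses, secondary in the Study Synopsis and Section D.

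**What to change.** In Section D, keep the fixed effects of Eq. 2 and pre-specify one of two bases for its test and confidence interval:

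1. variance robust at the overdose-cluster level, with a small-sample correction if clusters are few; or
2. the between-arm difference in clinician-level pre-to-post change in the proportion, with clustering by overdose cluster.

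The overdose cluster is the unit of randomization (Section C.b), and each clinician is assigned to only one. Inference at that level therefore covers repeat visits, pre/post pairing and shared clusters together. The second option also keeps the mean-proportion scale of Section D. The clinician-level comparison without overdose clusters was simulated; the robust variance was not, and the number of overdose clusters is not in the documents.

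A model with patient and patient-by-period random intercepts can be a sensitivity analysis. It needs no new identifiers: "Each patient and prescriber will be assigned a unique study identifier" (Section B.f).

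The cost is a few sentences in the plan, a little more analysis work, and a wider interval where visits are frequent and patients turn over. Separately, the plan should settle whether the proportion is of patients (Hypothesis 2), visits (Eq. 2) or prescriptions (the denominator stated in Section D).

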The goal of the project is to dampen the intensity and frequency of opioid prescribing and to increase awareness and use of medication assisted therapy for persons with opioid use disorder through a cluster randomized trial. Overdose notification letters (See Appendix 2 and 3) will be sent to primary care clinicians randomized to the experimental study arm and meeting inclusion criteria at AltaMed Health Services or Northwestern Medicine. Both letters will include "if/when/then" language which advises the clinician to keep the letter's recommendations close when their next patient presents with pain. Clinicians notified of their patient's overdose will be compared to a control group receiving guideline education and no notification of their patient's overdose (Appendix 6). To quantify the effect of the notification letter, we will measure the change in clinician weekly milligram morphine equivalent (MME) prescribed to all of their patients in 6-month periods before and after receiving overdose feedback letters. The secondary outcomes include the change in proportion of patients prescribed at least 50 daily MME, buprenorphine referrals for medication assisted therapy, and access rates for referral links included in the letter.

Because the letters include patient identifying information linked to outpatient prescribing records, we requested a HIPAA waiver of authorization to match outpatient records to mortality and non-fatal overdose records. The research could not feasibly be conducted if research participants' authorization were required. AltaMed will release information under the auspices of a waiver of HIPAA authorization. USC and AltaMed have a fully executed Business Associates Agreement, Memorandum of Understanding and Data Use Agreement; Northwestern and IDPH and USC and Northwestern have a fully executed Data Use Agreement. AltaMed and Northwestern will cede to the County IRB as the IRB of record for this study.

To create the list of overdose patients for whom opioids were prescribed, outpatient records will be linked to the emergency department and, in the case of Northwestern patients, IDPH death records. Overdose data will be linked with outpatient records using matching software that complies with institutional security and privacy standards at IDPH and Los Angeles County. Where an existing direct link code is available (e.g. MRN), we will use the code.

Primary hypotheses:

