discontinuation of opioids for persons whose most recent prescription exceeds 49 MME daily dose; or as reported to study staff (10).

If there is a significant difference in the prevalence of these adverse events or overdoses between the treatment and control groups, the differences will be reported to the Data and Safety Monitoring Board and in the publication of the study results. *It is important to note that prior quality evaluations of these letters observed no additional risk of abrupt changes to opioid prescribing upon receipt of a letter (<https://pubmed.ncbi.nlm.nih.gov/30093595/>).*

- Management of overdose and prescribing data poses no more than minimal privacy risks. USC, health systems and IDPH comply with all local and federal security regulations protecting privacy. Identified patient data will be destroyed after the notifications have been prepared. A HIPAA Limited Data Set that includes outpatient prescribing records, overdose events, and notification status will be transferred to USC for data analysis in USC's HIPAA compliant enclave.

b) Experimental Procedures:

Randomization and Allocation. Overdose clusters are the units of randomization in this study. A cluster consists of all clinicians who prescribed one or more of the included scheduled drugs to the patient in the year prior to the overdose. Overdose clusters will be randomized to the overdose notification group or the control group, stratified by the health system which defines the cluster in the year prior to the overdose event.

Allocation will be concealed until after the study groups are assigned. Clinicians who practice at multiple clinics will be assigned to the clinic at which the majority of their visits occurred in the year prior to the overdose event. If clinicians belong to more than one cluster (have multiple patients with opioid-related overdoses), they will be randomly assigned to one of those patients and placed in the corresponding study group. If clinicians belonging to more than one cluster are randomized to the intervention group, they will only receive an overdose notification regarding the one patient to whom they were randomly assigned.

Intervention. Clinicians in the intervention group receive a letter notifying them of their patient's fatal or non-fatal overdose. As described above, we will identify overdoses from electronic health record data from emergency departments and state vital records.

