2. **Avoid opioid prescribing for chronic pain and avoid/minimize opioid prescribing for acute pain.** According to the Centers for Disease Control and Prevention (CDC), clinicians should avoid opioids for chronic pain, and when necessary for acute pain, start with the lowest effective dose of immediate-release opioids. Three days or less is often sufficient to address acute pain. Opioids should not be considered first-line

or routine therapy for chronic pain.

3. **Taper opioids to safer doses.** The CDC recommends that for patients already on long-term high-dose opioid therapy, taper to a dose that is lower than 50 morphine milligram equivalents (MME) and consider slow opioid tapers as well as pauses in the taper if needed for long-term users.
4. **Avoid “the 90-day cliff.”** One California study found that nearly 70% of patients who died of prescription-related overdoses were prescribed scheduled drugs for 3 consecutive months.¹ The CDC recommends opioids should be discontinued if benefits do not outweigh risks (if realistic goals for pain and function have not been met).
5. **The CDC recommends prescribing naloxone** to patients on higher than 50 MME of opioids per day.
6. **Prescribed medications for opioid use disorder.** Clinicians should offer medications for opioid use disorder, such as buprenorphine/naloxone, to their patients with opioid use disorder. Physicians, physician assistants, and advanced practice nurses can file a waiver to prescribe buprenorphine for the indication of opioid use disorder by visiting the SAMHSA website (<http://www.samhsa.gov/medication-assisted-treatment/become-buprenorphine-waivered-practitioner>) or by calling SAMHSA at [contact]. On April 28, 2021, SAMHSA announced that it will waive the training requirement for physicians, physician assistants, and advanced practice nurses to become waivered to prescribe buprenorphine for the indication of opioid use disorder. Further, you can use the Epic Social Determinants of Health (at the bottom left of your Storyboard), click on “Select Community Resources”, and find “Substance Use” resources.

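### The high-dose rule in Eq. 2 tests a single prescription against 50 MME, but the stated outcome is the daily MME prescribed to the patient, so patients on concurrent opioids can be miscoded in either direction

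*Combined protocol and SAP*

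**What the plan says.** The outcome is named in two places. Among the secondary outcomes in the Study Synopsis (Section B.a) it is "the change in proportion of patients prescribed at least 50 daily MME". Hypothesis 2, under the heading for primary hypotheses, predicts "a greater reduction in the proportion of a clinician's patients prescribed at least 50 daily MME". In both places the quantity belongs to a patient and is a daily dose.

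It is made operational only in Section D, around Eq. 2. The dependent variable there is "whether the visit had a high dose prescription of 50 MME or greater (yes vs. no". The proportion to be reported is obtained by "dividing the total number of patient visits where an opioid of at least 50 MME was prescribed by the total number of opioid prescriptions". Both phrases refer to one prescription or one opioid, and neither says that the MME is per day. No section states how to combine two opioids held by one patient, whether ordered at one visit, at different visits or by different prescribers.

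The 50 MME level appears in two other places. Item 5 of the notification letters (Appendices 2 and 3) attaches it to "patients on higher than 50 MME of opioids per day". The adverse-event definition in Section C.a concerns "persons whose most recent prescription exceeds 49 MME daily dose".

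**The concern.** A patient's daily MME and the MME of a single order are the same thing only when the patient has one opioid. With two, the order-level test can disagree with the patient-level outcome at either time point, and the pre-to-post change inherits both errors. Hypothesis 2 would then be tested on a different quantity from the one it names. Item 3 of the letters is about bringing doses below this same level, so prescribing near the cut-point is what the endpoint has to record correctly. Two programmers working from the text could also build different variables, one testing each order and the other summing within the visit.

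**Working it through.** The plan gives no sample size, power or expected high-dose rate for this endpoint, so there is no planned figure to reproduce. The check applies the written rule to example records, then to a full grid, then to assumed dose distributions.

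**Two rules.** With a and b the daily MME of a patient's two concurrent opioids:
- Section D, read literally: high dose if max(a, b) ≥ 50.
- Synopsis and Hypothesis 2, read as the patient's daily dose: high dose if a + b ≥ 50.

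I take daily MME as intended in both. Without it, ten 5 mg hydrocodone tablets in one order would reach 10 × 5 = 50 MME on their own.

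**Conversions**, from the control-arm pocket guide: 60 mg oxycodone = 90 MME, so 90/60 = 1.5 MME per mg; one 5 mg hydrocodone tablet = 5 MME. For example, 30 mg oxycodone plus four such tablets is 45 + 20 = 65 MME/day.

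**Example records**

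| Before → after | Total | Section D rule | Summed rule |
|---|---|---|---|
| 45 + 20, unchanged | 65 | no | yes |
| 30 + 30 → 30 | 60 → 30 | no → no | yes → no |
| 60 + 20 → 45 + 20 | 80 → 65 | yes → no | yes → yes |
| 60 + 40 → 40 | 100 → 40 | yes → no | yes → no |

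The first two rows are missed high-dose patients, and the second is also an uncredited true fall. The third is a false exit. The fourth, a complete stop of the larger opioid, is coded correctly.

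**Grid.** All ordered pairs with each opioid from 5 to 100 MME in steps of 5, and every possible reduction or stop of one of the two:
- Of 364 pairs totalling 50 or more, 45 have both opioids below 50 and are missed; 364 − 45 = 319 are coded correctly.
- Of 8,160 cuts from those 364 pairs, 990 switch the Section D flag off while the total stays at 50 or more. All 990 start from a pair already coded high-dose, and none is a complete stop.
- 330 cuts bring the total below 50 without being credited. All start from pairs the rule had coded not high-dose.

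These counts show which errors are possible. They are not prevalences.

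**Denominator.** Take 100 visits: 10 with a single opioid at or above 50, 20 on 30 + 30, and 70 with a single opioid below 50. The Section D proportion is 10/(10 + 40 + 70) = 10/120 = 0.083. If one opioid is stopped in all 20 dual-opioid visits, it becomes 10/100 = 0.100, a rise. Under the summed rule per visit, the proportion falls from 30/100 to 10/100.

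**Size under assumptions not in the documents.** Main opioid lognormal with median 20-30 MME/day and log-SD 0.6-0.8; 10%-30% of patients with a second opioid of median 20 and log-SD 0.6; every patient cut by 25%; 400,000 simulated patients per scenario:
- The rule misses 9%-48% of patients truly at 50 or more.
- Of patients the rule counts as leaving high dose, 11%-41% are still at 50 or more if the larger opioid is cut, and 8%-27% if the main opioid is cut.
- The fall in the proportion is understated by about 0.1-1.9 points (larger opioid cut) or 0.2-2.1 points (main opioid cut). In the worst case of the first variant the true change is −7.1 points and the rule gives −5.2, so (7.1 − 5.2)/7.1 = 27% of the change is lost.

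**The case against.** Section D never says that concurrent orders are not to be summed, and its unit, the visit, leaves room to add up everything ordered that day. The adverse-event definition also uses a single prescription, so an order-level threshold may be deliberate. If prescriptions were the unit throughout, as in the denominator, order-level coding would be coherent. The synopsis calls the outcome secondary, and every figure on size rests on assumed doses.

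Part of this stands. The text can be read generously, the size is not evidence about this trial, and the problem should be solved together with the choice of unit and denominator. But summing within a visit still leaves opioids renewed at different visits unadded, and the numerator repeats the single-opioid test ("the total number of patient visits where an opioid of at least 50 MME was prescribed"). The safety definition serves a different purpose and does not alter the quantity in Hypothesis 2 ("the proportion of a clinician's patients prescribed at least 50 daily MME").

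A reader might infer three stronger things that the documents do not support:
- That every patient above 50 on two opioids is coded not high-dose. This is so only when neither opioid alone reaches 50.
- That cutting an opioid in those missed patients scores as success. A record already coded no cannot improve. False exits arise in other patients, those with an opioid at or above 50 that is lowered below 50 while the total is not.
- That the rule favours the letter arm. The simulations applied one common cut with no control arm, and their net effect was an understated fall. Eq. 2 is a group-by-time contrast, and nothing in the documents fixes the direction of bias in it.

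**Conclusion.** The operational rule in Section D does not measure the outcome named in the synopsis and Hypothesis 2 for patients on more than one opioid. It misses those whose opioids are each below 50 but total 50 or more, and does not credit their true falls below 50. In a separate group it credits exits that did not occur. The coding mismatch follows from the text read literally. How often it occurs depends on the share of patients with concurrent opioids and on their doses, neither of which is given; the 9%-48% miss share and the mostly understated fall hold only under the assumptions listed. Reductions concentrated on orders just above 50 could push the net effect the other way. No between-arm bias is shown. Clinician weekly MME, the main outcome, adds all MME and is untouched. The point should be corrected before analysis because the outcome carries a hypothesis listed as primary. It concerns outcome coding only and takes no position on any dose threshold.

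**What to change.** In Section D, use one definition for both the Eq. 2 indicator and the reported proportion. High dose: the summed daily MME of all distinct opioids that the clinician has prescribed to that patient and that are concurrently active is at least 50, with each order's daily MME = quantity × strength × conversion factor / days supplied.

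Three rules belong with it:
- An early refill or a replacement of the same opioid counts once, with the newer order superseding the older. Otherwise a 30 MME/day opioid refilled early would be counted as 60, and a 60 replaced by 45 as 105.
- The sum is restricted to the clinician's own orders, so that clinicians are not charged with the prescribing of others, possibly in the other arm. A version using all prescribers' orders in the EHR can be a sensitivity analysis.
- The denominator is in the same unit as the numerator (patients, if Hypothesis 2 stays as written), and the window in which orders count as concurrent is stated.

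The cost is a short paragraph in the plan and moderate programming on prescribing records that are already extracted. The small downside is that days supplied and overlap must be derived for each order, with a stated convention where days supplied is missing.
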